Urgency is associated with destructive, maladaptive behaviors that are common across types of mental illness. For example, urgency is robustly correlated with measures of aggression (13, 29, 30). Urgency is also strongly correlated with non-suicidal self-injury (NSSI) and with suicide attempts (13, 31), and there is evidence that NSSI mediates the relationship between urgency and attempting suicide (32). Many studies have found strong relationships between urgency and alcohol and cigarette use (33, 34) and drug use (35, 36). Beyond these cross-sectional findings, urgency prospectively predicts maladaptive behaviors and symptoms over time, suggesting that this form of impulsivity is not merely an artifact of other symptoms. Urgency predicts the first occurrence of NSSI (16), as well as increased urges to self-injure in the context of sad mood (37). Urgency also prospectively predicts increases in drug and alcohol use, as well as problems related to using alcohol (14, 35, 38). Other prospective studies find that urgency is predictive of a range of destructive behaviors, such as problem gambling (15), risky sexual behavior (38), and binge eating (15). Given its role in a wide range of maladaptive behaviors, urgency is an important transdiagnostic treatment target, yet few studies have evaluated whether this aspect of impulsivity is responsive to existing treatments. In one recent study, urgency at baseline was associated with worse treatment outcome for people with binge eating disorder (39). To assess how urgency responds to treatment of acute symptoms of psychopathology, the PI conducted a Preliminary Study (A) analyzing change in urgency in 348 patients seeking treatment in a partial hospitalization program. Results of this study showed that although urgency decreased following treatment, negative urgency levels on discharge day from the program correlated with depression (partial $r = .37$, $p < .001$) and modestly correlated with NSSI urges (partial $r = .17$, $p < .01$) and urges to use substances (partial $r = .18$, $p < .01$). Together, these findings suggest that individuals with higher levels of urgency may not respond to existing treatments, and individuals for whom existing treatment does not adequately improve urgency continue to struggle with associated clinical symptoms.

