
SPECIFIC AIMS

1. The first aim of this study is to confirm target engagement of cognitive control training at both the behavioral and neural levels of analysis in a clinical sample of patients reporting high levels of urgency. We predict that compared to the control group, patients completing cognitive training will show lower interference (improved behavioral performance) and decreased ERN and N2 amplitudes on a Stop-Signal response inhibition task.
2. The second aim is to examine clinical outcomes of cognitive control training. Based on Preliminary Study A, we predict that all patients receiving treatment at the BHP will report lower urgency scores at discharge; however, we predict that this decrease will be significantly greater in those receiving cognitive training. In addition, we predict that

participation in the training will be associated with greater reductions in depression symptoms, urges to engage in NSSI, and craving related to substance use.

3. The third aim is to assess this training's feasibility and acceptability to patients in a real-world clinical setting. We predict that at least 75% of enrolled patients will complete all training sessions.

SUBJECT SELECTION

This is a sub-study under the existing protocol entitled "Establishing the Effectiveness of Cognitive-Behavioral Partial Hospitalization for Anxiety, Depression, and Overall Functioning" (# 2010-P-001047/6). We will recruit 110 participants from the patient population at the McLean Hospital Behavioral Health Partial Hospital Program (BHP). Inclusion criteria include: (a) BHP patient, (b) score above a 3 on either the UPPS Negative Urgency Scale or the UPPS Positive Urgency Scale at admission, (c) able to complete a computer task for 15 minutes, and (d) consent to main BHP study protocol (# 2010-P-001047). Participants will be excluded from participation if they are experiencing acute symptoms of mania or psychosis; if they are currently undergoing ECT; or if they have a history of a traumatic brain injury. Participants who are left-handed will be excluded from the EEG portion of the study but will be allowed to complete all other portions of the study.

Additional inclusion criteria for the research study will be consistent with admission criteria for the BHP program. Specifically, patients who are acutely psychotic and are deemed unfit for admission at the BHP will not be invited to participate in this study.

SUBJECT ENROLLMENT

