Baseline and Post-Training Research Assessment. All participants will complete a baseline assessment of symptoms, craving for substances, and cognitive control. Participants deemed eligible for the EEG portion of the study will complete one additional session on the day of the baseline assessment and one additional session on the day of the post-training assessment, which

will include high-density ERP data during completion of one of these cognitive tasks. Baseline assessments will take place on the day following admission or on the following day (3rd day). The tasks at baseline and post-training will include:

Self-Report and Interview Measures

- a. Negative and Positive Urgency Scales are subscales of the UPPS-P, a multidimensional impulsivity self-report measure (56, 27). These scales reflect impulsive response to negative and positive emotions, respectively. The Negative and Positive Urgency scales are often highly correlated, and factor analysis has found that these dimensions share a common underlying construct of emotion-related impulsivity (57).
- b. Alexian Brothers Urge to Self-Injure Scale (ABUSI; 60) is a brief self-report measure that assesses frequency and intensity of urges to engage in NSSI.
- c. Craving Scale (based on [61]) is a 3-item scale predictive of future substance use for substances such as alcohol, opioids, and cocaine (61-63). Patients will rate their craving for their primary substance of choice.
- d. Positive and Negative Affect Scale-10 item (PANAS-10; 69), a ten-item questionnaire assessing current positive and negative emotions. This scale will also be administered at the beginning of each of the training sessions.
- e. Distress Intolerance Index (DII; 70), a ten-item self-report measure assessing perceived ability to tolerate distressing physical and emotional states.
- f. Ruminative Responses Scale (RRS; 71), a self-report measure of thinking styles in response to negative mood.
- g. Attentional Control Scale (ACS, 72); a brief self-report measure of cognitive control.
- h. Edinburgh Handedness Inventory-Short Form (74). At the baseline session only, participants will complete a 4-item measure to determine handedness.
- i. Debriefing. At the post-training session only, participants will complete a debriefing questionnaire to assess their perceptions of the study.

Participants will also complete two measures that are already administered as part of standard clinical care at the BHP:

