Sessions will be completed during the lunch hour, in between groups, or at the end of the day. Sessions will begin on the second or third day and continue until discharge. The average length of stay in the BHPP is 8.5 days. Sessions will be completed in the BHP computer lab, where patients complete daily progress monitoring as part of their standard clinical care, or a private room when available. A member of the study staff, typically the research coordinator, will set up the computer task and be available for any questions or problems.

BIOSTATISTICAL ANALYSIS: ERP data will be pre-processed to remove artifacts (e.g., by using independent component analyses) and identify ERPs using BrainVision Analyzer. Hypothesis 1 will be tested using a 2 (condition: TAU+training, TAU) x 2 (time: baseline, discharge) mixed-model analysis of variance (ANOVA) with Stop-Signal Reaction Time as the dependent variable; two separate ANOVAs with the same predictors will also test dependent variables of ERN and N2 amplitudes. Hypothesis 2-3 will be similarly tested via mixed-model ANOVA with the same predictors; one model will test the DV of Negative Urgency; one will test the model of Positive Urgency; and three models will test change in craving, depression, and self-harm urges. Hypothesis 4 will be tested via descriptive statistics assessing the percentage of enrolled participants who complete the training intervention and their mean level of satisfaction at discharge. Analyses will consider the impact of several a priori potential confounds on effects of the intervention, using Pearson correlations to test if performance on cognitive tasks are related to age, medication, primary diagnosis, or percentage of completed training sessions. If significant correlations are identified, these variables will be included in the above analyses as covariates.

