Power analysis: A priori power analysis conducted in G*Power indicated that a sample size of 68 individuals is necessary to achieve adequate power ($1 - \beta = 0.9$) to detect small to medium effects (Cohen's $f = 0.2$) in repeated-measures ANOVA. To ensure adequate power, we will recruit up to 90 patients to begin the study, based on predicted attrition rates (see "Potential Problems and Alternate Strategies"). To complete recruitment within two years, we will enroll 3.75 patients per month, or roughly one per week. In previous cognitive training studies conducted by [name] in the BHP, she has successfully enrolled patients at a rate of one per week, indicating that the target in the present study is highly feasible.

RISKS AND DISCOMFORTS

Potential Risks

i. **Privacy and Confidentiality of Data:** As with all research, there is a risk of loss of confidentiality and/or breach of data security. Given the substantial measures put in place to protect privacy and confidentiality within the BHP's clinical research program (described

above), there is a low likelihood of this risk.

ii. Frustration: The behavioral tasks that are administered at the baseline, training sessions, and discharge session require sustained concentration and focus. These tasks are relatively demanding by design, and thus some participants may feel moderately frustrated by the challenging nature of the tasks. However, in order to appropriately engage the putative underlying mechanisms of response inhibition and working memory capacity, it is necessary to include tasks that assess participants' ability to effectively recruit these domains under somewhat challenging conditions. Thus, there is a moderate possibility of frustration after completion of these tasks for some individuals.

iii. Fatigue: Participants may become tired following completion of relatively demanding cognitive tasks that require sustained concentration and focus. This may be particularly true for participants randomized to the TAU+training condition, as this condition involves up to 10 sessions of 15-minute cognitive exercises. It is likely that some participants may feel mentally fatigued after completion of such training sessions.

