**Date: 2/19/2021**

**NCT#: NCT03527550**

The statistical analysis plan for primary outcome measures is as follows:

1. Change in Average Score on Negative Urgency Scale:

*A 2 (condition: TAU, TAU + cognitive training) x 2 (time) repeated-measures Analysis of Variance (ANOVA) will be used to test change in negative urgency at time 1 (admission) and time 2 (discharge), and whether participants differ in their average change in negative urgency as a function of condition (interaction of condition X time).*

2. Change in Average Score on Positive Urgency Scale:

*A 2 (condition: TAU, TAU + cognitive training) x 2 (time) repeated-measures Analysis of Variance (ANOVA) will be used to test change in positive urgency at time 1 (admission) and time 2 (discharge), and whether participants differ in their average change in positive urgency as a function of condition (interaction of condition X time).*

Statistical Analysis Plan for Secondary Outcome Measures:

1. Change in Estimated Stop-Signal Reaction Time (SSRT) on Stop-Signal Task (ms):

*A 2 (condition: TAU, TAU + cognitive training) x 2 (time) repeated-measures Analysis of Variance (ANOVA) will be used to test change in SSRT at time 1 (admission) and time 2 (discharge), and whether participants differ in their average change in SSRT as a function of condition (interaction of condition X time).*

2. Feasibility of assessing change in event-related potentials (ERPs) during a Stop-Signal Task in a partial hospital population:

*This will be tested using descriptive statistics assessing the percentage of participants who are able to complete and provide ERP data for the stop-signal task.*

3. Completion Rates:

*This will be tested using descriptive statistics assessing the percentage of enrolled participants who complete the training intervention and the discharge session. This will be compared to an a priori benchmark of a 75% completion rate, based on previous studies.*

4. Average Perceived Helpfulness of Training

*This will be tested using descriptive statistics assessing the average rating of overall perceived helpfulness of the intervention, as rated by participants using a self-report form at the discharge session. This average rating will be compared to an a priori benchmark of an average rating of 4.0 or greater for each of the two training tasks (PASAT and Go/NoGo).*

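### Two unranked primary outcomes are tested separately with no stated alpha or success rule, while the sample size of 68 matches one unadjusted test

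*Protocol*

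**What the plan says.** The Protocol's power paragraph "indicated that a sample size of 68 individuals is necessary to achieve adequate power". It gives power 0.9, f = 0.2 and a repeated-measures ANOVA in G*Power. It does not name the outcome, the effect within the ANOVA, the alpha or the correlation between baseline and discharge. Up to 90 patients are to be randomised so that at least 68 complete.

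The SAP opens in the plural: "The statistical analysis plan for primary outcome measures is as follows". Item 1 tests "whether participants differ in their average change in negative urgency as a function of condition (interaction of condition X time"; item 2 tests "whether participants differ in their average change in positive urgency as a function of condition (interaction of condition X time". The items are numbered but not ranked. The Protocol's Biostatistical Analysis section likewise gives each scale its own model: "one model will test the DV of Negative Urgency; one will test the model of Positive Urgency".

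Two other places bear on how the results may relate. The measures section says "The Negative and Positive Urgency scales are often highly correlated", without a figure. Subject Selection requires only a "score above a 3 on either the UPPS Negative Urgency Scale or the UPPS Positive Urgency Scale at admission", so a patient may be elevated on one scale alone. Specific Aim 2 predicts a significantly greater fall in urgency with training but does not say on which scale, or whether on both.

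**The concern.** One sample size supports two primary tests, and nothing says how the two results combine into a verdict. Several rules fit the text: either scale at 0.05, either scale with adjustment, both scales, or one scale ahead of the other. They differ in error rate and in power.

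Suppose positive urgency gives p = 0.04 and negative urgency p = 0.30. That is a success if either scale at 0.05 is enough. It is a failure if both are required, and a failure under Holm, because 0.04 exceeds 0.025. Under a fixed order it depends on which scale goes first. With no rule written down, the reading can be chosen after the results are known.

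**Working it through.** **Inputs from the documents.** N = 68 completers, 1:1 allocation (34 per arm), two time points, f = 0.2, target power 0.9.

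**Assumed, because the documents do not give them.** Alpha 0.05 (the F test is non-directional); pre-post correlation rho = 0.5, with 0.3 and 0.7 as a range; equal SDs at both times; correlation r between the changes on the two scales of 0.5 / 0.7 / 0.9.

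**Step 1: reproduce 68.** For the condition-by-time interaction with two groups and two times, the noncentrality is lambda = N × 2 × f² / (1 − rho), with 1 and N − 2 degrees of freedom.

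- lambda = 68 × 2 × 0.04 / 0.5 = 10.88. Power at alpha 0.05 is 0.9015, which matches the plan.
- At rho 0.3, lambda = 7.77 and power is 0.784. At rho 0.7, lambda = 18.13 and power is 0.987.
- The time main effect also gives 68. The between-group main effect gives 200 and does not match.

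So 68 fits a single unadjusted test, apparently the interaction.

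**Step 2: two tests.** In a 2 × 2 design the interaction F equals the squared t on change scores. At f = 0.2 and rho = 0.5 the difference in change is 0.8 SD. Pairs of t statistics with 34 per arm were simulated from correlated normal changes. The family error rates in the first and fourth rows assume no effect on either scale; the other rows assume f = 0.2 on both.

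| Quantity at 68 completers | r = 0.5 | r = 0.7 | r = 0.9 |
|---|---|---|---|
| No effect: at least one p < 0.05 | 9.1% | 8.4% | 7.1% |
| Both p < 0.05 | 83% | 85% | 87% |
| Exactly one p < 0.05 | 13% | 11% | 6% |
| No effect: at least one p < 0.025 (Holm family error) | 4.7% | 4.3% | 3.6% |
| At least one p < 0.025 (Holm, some success) | 94% | 92% | 88% |
| Holm, power for a named scale | 88% | 88% | 87% |

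The first and fourth rows do not depend on rho. The power rows do: with both scales required, power is 66% to 73% at rho 0.3 and about 98% at rho 0.7.

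**Step 3: completers for 90% power when both are required.** At rho 0.5, 82 / 80 / 76.

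**The case against.** The strongest reply is that the scales measure nearly the same thing, so two tests are little more than one, and that a small early trial can take 0.05 as understood. Part of this stands. Correlation shrinks the problem: independent tests would give 1 − 0.95² = 9.75%, against 7.1% at r = 0.9. It does not remove it. An understood alpha of 0.05 also does not say whether one or both scales must succeed. The SAP calls both outcomes primary and tests each, so a rule is needed to read them.

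A reader might infer more than the documents support, in three ways.

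- **That 68 is wrong.** It is not. It reproduces, and it stands for one scale tested alone or first.
- **That adjusting for two scales costs power the trial cannot spare.** At 0.025 the power for one named scale is 84.0%, and 82 completers would be needed for 90%. But where either scale can carry the claim, the relevant figure is the chance of at least one success. At 68 that is 94% / 92% / 88% under Holm, with family error below 5%. It is therefore untrue that 90% power at 5% error is available only by testing one scale first or alone.
- **That the documents settle which scale ranks first.** Negative urgency is listed first, and the Protocol's background reports that "negative urgency levels on discharge day from the program correlated with depression". No comparable positive-urgency correlations are given there, and the second preliminary study reports only urgency as a whole. This favours negative urgency but does not decide it.

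**Conclusion.** The concern holds as a gap in the decision rule with a measurable consequence. Reading either scale at 0.05 as success puts the family false-positive rate at about 7% to 9%. Requiring both puts power at 68 at about 83% to 87%, below the stated 90%. Even when both effects are real, the two tests disagree in about 6% to 13% of trials, and the plan has no answer for that case.

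These figures rest on assumed values of alpha, rho and r. The power and disagreement figures also assume f = 0.2 on both scales, which the either-scale entry criterion makes uncertain. If only one scale truly responds, a both-required rule succeeds at most about 5% of the time. Holm keeps at least 84.0% for the responding scale, if its effect is f = 0.2 and rho is 0.5.

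**What to change.** Before any between-arm comparison of urgency, add to the SAP a two-sided family alpha of 0.05 and one success rule:

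- **(a) Holm across the two scales.** Either scale can carry the claim. The smaller p-value is compared with 0.025 and, if it passes, the other with 0.05.
- **(b) Fixed order.** One scale is tested at 0.05 and decides the trial; the second is confirmatory only if the first is significant. This keeps 90% power for the first test at rho 0.5. The price is that a result on the second scale alone cannot be claimed. The sponsor should choose the order and give its reason.

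If both scales are to be required, no alpha adjustment is needed, but the power at 68 should be restated as about 83% to 87% under the assumptions above.

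In the Protocol's power paragraph, state the test, alpha and rho behind 68, and give the power at rho 0.3 and 0.7 (78% and 99%).

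The Protocol's monitoring section has the PI test baseline-to-discharge change on self-report symptom measures in both groups every twelve months. It does not say whether urgency is included. Confirm whether urgency has already been compared between arms and, if so, disclose it beside the new rule.

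The cost is one SAP paragraph, a sentence or two in the power section and one disclosure. Neither (a) nor (b) needs extra patients.

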**Date: 2/19/2021**

**NCT#: NCT03527550**

The statistical analysis plan for primary outcome measures is as follows:

1. Change in Average Score on Negative Urgency Scale:

*A 2 (condition: TAU, TAU + cognitive training) x 2 (time) repeated-measures Analysis of Variance (ANOVA) will be used to test change in negative urgency at time 1 (admission) and time 2 (discharge), and whether participants differ in their average change in negative urgency as a function of condition (interaction of condition X time).*

2. Change in Average Score on Positive Urgency Scale:

*A 2 (condition: TAU, TAU + cognitive training) x 2 (time) repeated-measures Analysis of Variance (ANOVA) will be used to test change in positive urgency at time 1 (admission) and time 2 (discharge), and whether participants differ in their average change in positive urgency as a function of condition (interaction of condition X time).*

Statistical Analysis Plan for Secondary Outcome Measures:

1. Change in Estimated Stop-Signal Reaction Time (SSRT) on Stop-Signal Task (ms):

*A 2 (condition: TAU, TAU + cognitive training) x 2 (time) repeated-measures Analysis of Variance (ANOVA) will be used to test change in SSRT at time 1 (admission) and time 2 (discharge), and whether participants differ in their average change in SSRT as a function of condition (interaction of condition X time).*

2. Feasibility of assessing change in event-related potentials (ERPs) during a Stop-Signal Task in a partial hospital population:

*This will be tested using descriptive statistics assessing the percentage of participants who are able to complete and provide ERP data for the stop-signal task.*

3. Completion Rates:

*This will be tested using descriptive statistics assessing the percentage of enrolled participants who complete the training intervention and the discharge session. This will be compared to an a priori benchmark of a 75% completion rate, based on previous studies.*

4. Average Perceived Helpfulness of Training

*This will be tested using descriptive statistics assessing the average rating of overall perceived helpfulness of the intervention, as rated by participants using a self-report form at the discharge session. This average rating will be compared to an a priori benchmark of an average rating of 4.0 or greater for each of the two training tasks (PASAT and Go/NoGo).*

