The proposed research plan will strictly adhere to the data and safety monitoring guidelines set forth by McLean Hospital and Partners Healthcare. As the proposed study is a relatively small clinical trial that does not meet the definition of an NIH-defined Phase III clinical trial, and given the relatively low risk to study participants, we have not proposed a full Data Safety and Monitoring Board for the present study. However, we will implement a series of data and safety monitoring procedures to ensure optimal safety for all participants. The Principal Investigator ([name]) and the study sponsor ([name]) will hold responsibility for monitoring the safety of study participants and the security of data collected in this study.

Safety monitoring will be conducted on an ongoing basis via several procedures. First, participants' self-report measures include data that indexes patient safety (i.e., suicidal ideation, self-harm urges), and these measures will be reviewed daily by a member of study staff. If participants report an increase in risk based on these measures, the study staff member will immediately contact the PI. Also, members of study staff will inform the PI of any participants who verbally report any new safety concerns (either during the clinical interview or during routine study procedures). Any adverse events or serious adverse events will be reported to the Partners Healthcare Institutional Review Board (IRB). In accordance with Partners Healthcare policy, any unanticipated problems or adverse events will be reported within 5 working days or 7 calendar days from the date the problem is discovered. Serious adverse events would be reported within 24 hours of discovery.

In addition to these ongoing safety procedures, the PI will conduct a review of specific data points relevant to patient safety every twelve months. This review will encompass a statistical test of changes in symptoms on self-report measures from baseline to discharge in both

the TAU and the TAU+training groups. This will allow for evaluation of any potential negative effects arising from participation in the training program.

REFERENCES

1. Johnson, S. L., Tharp, J. A., Peckham, A.D., Sanchez, A.H., & Carver, C.S. (2016). Positive Urgency is related to difficulty inhibiting prepotent responses. *Emotion*, 16: 750-759.

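### The condition × time tests of urgency and SSRT are change-score tests; adjusting for the time-1 score already collected would give a modest gain in precision without new data

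*SAP*

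**What the plan says.** The SAP gives primary outcome 1 (negative urgency) a 2 × 2 model: "repeated-measures Analysis of Variance (ANOVA) will be used to test change in negative urgency at time 1 (admission) and time 2 (discharge". Primary outcome 2 is worded alike: its ANOVA "will be used to test change in positive urgency at time 1 (admission) and time 2 (discharge". Secondary outcome 1 (SSRT) repeats the form. In each case the treatment effect is the condition × time interaction.

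Neither document adjusts for the outcome's own time-1 score. The protocol's Biostatistical Analysis section considers other covariates, "using Pearson correlations to test if performance on cognitive tasks are related to age, medication, primary diagnosis, or percentage of completed training sessions", and adds them only if a correlation is significant.

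Four other places bear on the point:

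- Power analysis (protocol): "a sample size of 68 individuals is necessary to achieve adequate power", for power 0.9 at Cohen's f = 0.2. Alpha and the pre-post correlation are not stated.
- Subject Selection (protocol): eligibility requires a "score above a 3 on either the UPPS Negative Urgency Scale or the UPPS Positive Urgency Scale at admission".
- Self-Report and Interview Measures, item a (protocol): "The Negative and Positive Urgency scales are often highly correlated".
- Specific Aims, aim 2 (protocol): "we predict that all patients receiving treatment at the BHP will report lower urgency scores at discharge", with a larger fall expected under training.

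**The concern.** With two time points, the interaction contrast is the difference between arms in mean change. That fixes the coefficient on the time-1 score at 1. When discharge scores regress toward the mean (a pre-post slope below 1), the change score carries noise from time 1 that an estimated coefficient would remove. The usual remedy is to regress the discharge score on condition and the time-1 score. This costs one degree of freedom and uses data already in hand.

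At stake is the width of the interval around the between-arm difference, in a trial aiming for only 68 participants with both measures. Neither the validity of the test nor the stated power is in question.

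**Working it through.** **Inputs from the documents.** N = 68 completers, equal allocation (34 per arm), f = 0.2, power 0.90, two times, two arms.

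**Assumptions (not in the documents).** Two-sided alpha 0.05; rho, the pre-post correlation before selection, with equal SDs at both times; r, the correlation between the two urgency scales; the fraction selected by the eligibility cut (top 10–30%); normal scores.

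**1. The plan's own figure.** For the within-between interaction, lambda = f² × N × 2/(1 − rho). At rho = 0.5: 0.04 × 68 × 2/0.5 = 10.88. With F on 1 and 66 df, power is 0.9015, so N = 68 reproduces. In this model f = 0.2 is a between-arm difference in change of 4f = 0.8 within-cell SD. At rho 0.3 the same formula needs 94 participants, and at rho 0.7 it needs 42, so 0.5 is the value that fits.

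**2. Equivalence.** On one simulated data set of 34 per arm, the interaction F and the squared two-sample t on change scores were both 5.0235.

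**3. Variance per person** (unselected SD = 1, Vx = variance of the time-1 score in the trial):

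- change score: (1 − rho)² × Vx + (1 − rho²)
- adjusted: 1 − rho²
- ratio: (1 + rho)/[(1 − rho) × Vx + 1 + rho]

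With Vx = 1 the ratio is (1 + rho)/2. Estimating the slope at N = 68 multiplies it by about 1 + 1/(68 − 4) = 1.0156. CI narrowing is 1 − √(ratio).

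**4. Vx.** SSRT is not a selection variable, so Vx = 1. Urgency is selected on either scale. From 4,000,000 bivariate normal draws with r 0.7–0.9, Vx is 0.26–0.51 if 10–30% exceed the cut on each scale, and 0.25–0.48 if 10–30% qualify on either scale. The span used is 0.25–0.51.

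**5. Results, slope cost included.**

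| rho | SSRT ratio | SSRT CI narrower by | Urgency ratio (Vx 0.51 to 0.25) | Urgency CI narrower by |
|---|---|---|---|---|
| 0.3 | 0.660 | 18.8% | 0.797 to 0.895 | 10.7% to 5.4% |
| 0.5 | 0.762 | 12.7% | 0.868 to 0.938 | 6.8% to 3.2% |
| 0.7 | 0.863 | 7.1% | 0.932 to 0.973 | 3.5% to 1.4% |
| 0.8 | 0.914 | 4.4% | 0.961 to 0.988 | 2.0% to 0.6% |
| 0.9 | 0.965 | 1.8% | 0.989 to 1.002 | 0.5% to −0.1% |

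Example, urgency at rho 0.5 and Vx 0.51: 1.5/(0.255 + 1.5) = 0.855; × 1.0156 = 0.868; 1 − √0.868 = 6.8%.

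In participants, for SSRT the change-score test would need about 68/0.762 = 89 (rho 0.5) or 68/0.914 = 74 (rho 0.8) to match the adjusted analysis at 68. For urgency the figures are 68/0.868 = 78 down to 68/0.988 = 69. For SSRT at rho 0.5 and a 0.8 SD difference, power moves from 0.90 to 0.96.

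**6. If time 1 is the baseline session.** Suppose the screening score correlates q = 0.7–0.9 with a separate score at that session, and that discharge depends on screening only through that score. Then Vx becomes q² × Vx + 1 − q². With the top 25% selected, screening Vx of 0.31–0.47 becomes 0.81 × 0.31 + 0.19 = 0.44 to 0.49 × 0.47 + 0.51 = 0.74. At rho 0.5 the narrowing rises from 4.1–6.3% to 5.9–9.7%; at rho 0.8, from 0.9–1.8% to 1.6–3.1%.

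**The case against.** The strongest reply is that this is preference. The outcomes are named as changes, the ANOVA estimates change directly, the time-1 score is already in the model as a response, and the same ANOVA supplies the time effect that aim 2 predicts. Much of that stands: the planned test is sound, and a discharge-on-condition model cannot test whether all patients improve. But having the time-1 score as a response with its coefficient fixed at 1 is not adjustment for it, and a precision gain that needs no new data is worth considering even where nothing is wrong.

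Three further objections stand and limit the claim.

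- A reader might infer that adjustment wins whenever the slope is below 1. That is a large-sample statement. At N = 68 and rho 0.9 the urgency ratio is about 0.99–1.00. The documents give neither rho nor r, so every percentage here is conditional.
- Time 1 for urgency is ambiguous. Screening uses the admission score; the protocol also lists the urgency scales at the baseline assessment on the second or third day; the SAP says admission. The SAP uses that same word for SSRT, a study task that can only follow consent, so its wording does not settle the matter.
- Under randomisation both analyses target the same between-arm effect, but up to 90 are randomised for at least 68 with both measures, a possible loss of 22/90 = 24%. If dropout is related to baseline, the two estimates can differ among completers.

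**Conclusion.** The point holds as an optional efficiency improvement. All three interaction tests are change-score tests without adjustment for the outcome's own time-1 score. For SSRT the gain is about 4–13% in CI width at rho 0.5–0.8 (about 19% at 0.3, 2% at 0.9). For the two primary urgency outcomes it is about 1–7% at rho 0.5–0.8 and r 0.7–0.9 (roughly 5–11% at 0.3, essentially nil at 0.9), and somewhat more if time 1 is the day 2–3 session. These figures rest on the assumed rho, r, selected fraction and normality.

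Two stronger readings are not supported. A reader might infer that the plan is invalid or underpowered, but the test is valid under randomisation and N = 68 reproduces under alpha 0.05 and rho 0.5. A reader might also apply the textbook 25% variance saving at rho 0.5 to urgency, but that ignores selection on admission urgency and the high correlation between the scales.

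**What to change.** - For negative urgency, positive urgency and SSRT, take the between-arm estimate from the discharge score regressed on condition and that outcome's time-1 score, or from a mixed model on both visits with a common baseline mean. Report the adjusted difference with its 95% CI.
- State which urgency assessment is time 1, and reconcile the SAP with the protocol's Subject Selection section and its baseline assessment section.
- Keep the 2 × 2 ANOVA for the time effect in aim 2 and as a sensitivity analysis of the interaction.
- Note that the two estimates can diverge among completers, and that the mixed model also uses dropouts' time-1 scores and so has a different analysed set.
- Make the change before outcomes are compared by arm. The protocol's Monitoring and Quality Assurance section plans a review every twelve months covering both groups: "This review will encompass a statistical test of changes in symptoms on self-report measures from baseline to discharge". The documents do not show whether such a review had already compared urgency by arm. If one had, say so and present the adjusted estimate as supportive.

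The cost is SAP wording, a short code change and one degree of freedom. No new data are needed.
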